Statistical Considerations	
Below is a summary of the statistical methods. Further details can be found in Section 8.
 
Two analyses are planned: 1) an interim analysis to select the POC dose based on the MAD data; and 2) a final analysis at study completion. Additionally, DMC safety analyses will be performed for each MAD cohort and throughout the POC to monitor patient safety as described in the DMC charter. An additional analysis may be performed for the MAD portion of the study when all MAD patients have completed the safety follow-up, or withdrawn from the study, and prior to the final analysis. Data from the POC part of the study will be excluded from this additional analysis.
 
Unless stated otherwise, statistical testing will only be performed on the POC data and will be done using 2-sided overall alpha of 0.10. Data will be summarized descriptively by treatment and overall for each study phase. For the MAD portion, BOS161721 will be summarized overall and by each dose level and placebo patients from each cohort will be combined.
 
The descriptive summaries for the categorical data will include number and percentage. The descriptive summaries for the continuous data will include number, mean, median, standard deviations (SD), 25th and 75th percentiles, minimum, median, and maximum. Counts, medians, 25th and 75th percentiles, and standard error will be presented for time-to-event data.

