2.2 Phase 2 Proof of Concept

OBJECTIVES	ENDPOINTS
Primary	

 • To demonstrate a superior effect of BOS161721 at the chosen dose compared with placebo for response on the SRI-4 	Primary Efficacy Endpoint 
 • The proportion of patients with a SRI-4 response at Day 210 (see Section 6.3.4.1)
Secondary	

 • To demonstrate a superior effect of BOS161721 at the chosen dose compared with placebo for response on clinical indicators of SLE activity, in adult patients with moderately to severely active SLE on limited background standard of care treatment 	Secondary Efficacy Endpoints 
 • The proportion of patients with: 
 - SRI-4 response at each visit - SRI-5 and SRI-6 response at each visit (Section 6.3.4.2) - a sustained reduction from baseline of oral corticosteroid (CS) (≤ 7.5 mg/day and $<$ Day 0 dose) between Day 150 and Day 210 - new or recurrent BILAG flares (≥ 1 qualifying BILAG A or > 1 qualifying BILAG B) through Day 210 - PGA worsening - a BICLA response - a CLASI response

	
 - medication failures • The changes and percent changes from baseline in: 
 - CLASI - PGA - Total number of swollen joints, tender joints, and active joints (swelling and tenderness in the same joint) in the ACR-28 joint count - SLEDAI-2K - SLICC/ACR damage index • Time to medication failure • Group mean percent reduction in CS administration from baseline Day 0 dose through Day 210 in patients receiving ≥ 7.5 mg/day prednisone equivalent at Day 0 • Duration of longest SRI-4 response • Time to first BILAG flare (≥ 1 new or recurrent BILAG A or > 1 new or recurrent BILAG B) relative to baseline through Day 210
--	--

Safety

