8 STATISTICS

The following analyses are planned:

- An IA will be performed during the last cohort of the MAD portion to determine dose selection for the POC part of the study.
- An additional analysis may be performed for the MAD portion of the study when all MAD patients have completed the safety follow-up or withdrawn from the study, and

prior to final analysis. Data from the POC part of the study will be excluded from this additional analysis.

- The final analysis will be performed when all patients have completed the POC safety follow-up or withdrawn from the study.
- Safety analyses will be performed for DMC reviews throughout the study to evaluate dose escalation decisions and accumulating safety data. The frequency and details of the content and format of the safety review meetings will be described in the SAP and/or DMC charter.

All statistical analyses will be performed using Statistical Analysis Software (SAS®) Version 9 or higher.

The following standards will be applied for the analysis unless otherwise specified. Data will be summarized descriptively by treatment and overall for each study portion. For the MAD part of the study, BOS161721 will be summarized overall and by each dose level, and placebo patients from each cohort will be combined. Select parameters may be summarized using patients from both study parts. Statistical testing will be performed on data from the phase 2 portion only.

Continuous data will be summarized using number, mean, standard deviation (SD), 25th and 75th percentiles, minimum, median, and maximum. Categorical data will be summarized by treatment group using frequency tables (number and percentage). Time to event data will be summarized using counts, medians, 25th and 75th percentiles, and standard error. All data will be listed for all patients.

Statistical inference will be based on a 2-tailed test with an overall 0.10 level of significance, unless stated otherwise.

The effects of noncompliance, background therapy use, treatment discontinuations, premature withdrawal from study and covariates will be assessed to determine the impact on the general applicability of results from this study. Exploratory analyses of the data will be conducted as deemed appropriate. Any deviations from the planned analyses will be described and justified in the final integrated CSR.

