8.1 Sample Size

Sample size in the phase 1b part of the study is based on operational consideration.

The sample size in the phase 2 portion is based on the primary endpoint, SRI-4 Response at Day 210. Based on efficacy data from a recently completed study with Ustekinumab⁵¹, where the primary endpoint was also SRI-4, the sample size in the phase 2 part of the BOS161721-02 study is set at 96 evaluable patients. In the

Ustekinumab study of 102 patients, a statistically significant difference in SRI-4 response was shown in favor of Ustekinumab (62% of Ustekinumab treated patients achieved SRI-4 response vs. 33% in patients receiving placebo). The Ustekinumab phase 2 study is an appropriate comparator to BOS161721-02 because both studies share the same primary endpoint of SRI-4 response and BOS161721 and Ustekinumab have overlapping mechanisms of action (T follicular helper and Th17 cell biology).

Approximately 110 additional patients will be randomized in a 2:1 ratio to BOS161721 versus placebo to achieve approximately 96 evaluable patients in the FAS of the phase 2 portion. This assumes 14 patients will drop prior to having received treatment or having completed a post-baseline efficacy measure. Enrollment and randomization will be monitored in a blinded fashion and may be increased if needed to ensure at least 96 evaluable patients are randomized into the FAS.

A total of 96 evaluable patients randomized provides 80% power to detect a treatment difference of 29% in SRI-4 response rates at Day 210, based on a targeted 2-sided significance level of 10% and using a 2-sided Pearson's chi-squared test. This assumes a response rate of 62% for BOS161721 and 33% for placebo.

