8.2.3 Primary Efficacy Endpoint(s)

The proportion of patients who achieve a SRI-4 response at Day 210 will be assessed via Pearson's chi-squared analysis. The primary efficacy endpoint will be analyzed using the FAS and if needed repeated in the PP analysis set. Missing values will be addressed by employing a last observation carried forward (LOCF) analysis. Other imputation methods may be employed as a sensitivity analysis and will be described in the SAP. Analyses based on observed values may also be performed.

Exploratory subgroup analyses assessing impact of baseline factors such as baseline disease severity, background therapy, race, geography, baseline serologic activity and other characteristics may be performed. Additional exploratory analyses of disease activity endpoints may be performed based on emerging data.

Patients that received prohibited medications or unallowable CS usage as described in [Section 4.6](#) will be considered "medication failures" and will be treated as statistical non-responders at time points on or following the first date of prohibited medication or unallowable CS usage for the primary efficacy analysis. The determination of medication failures will be reviewed using blinded data and finalized prior to unblinding.

The superiority of BOS161721 relative to placebo will be evaluated. If the proportion of SRI-4 responders for the selected POC dose in BOS161721 arm is higher than that of the placebo arm, then BOS161721 will be considered superior to placebo if the 2-sided p-value is < 0.10 . Secondary and exploratory endpoints for this POC portion will be evaluated based on the same statistical hypothesis.

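### The two-sided 0.10 level called 'overall' is the error rate of the primary SRI-4 Day 210 test only, because the same superiority hypothesis is applied ungated to all secondary and exploratory endpoints

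*Protocol*

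**What the plan says.** All references are to the current protocol text, version 7.0.

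- **Protocol Summary, Statistical Considerations:** "statistical testing will only be performed on the POC data and will be done using 2-sided overall alpha of 0.10". The sentence opens with an exception for anything stated otherwise.
- **Section 8:** "Statistical inference will be based on a 2-tailed test with an overall 0.10 level of significance, unless stated otherwise".
- **Section 8.2.3:** if the SRI-4 response rate is higher on the drug arm, "BOS161721 will be considered superior to placebo if the 2-sided p-value is < 0.10". The next sentence reads: "Secondary and exploratory endpoints for this POC portion will be evaluated based on the same statistical hypothesis".
- **Section 2.2, secondary objective:** "To demonstrate a superior effect of BOS161721 at the chosen dose compared with placebo for response on clinical indicators of SLE activity". The primary objective uses the same verb.
- **Section 2.2, secondary endpoints:** a long list, including "SRI-5 and SRI-6 response at each visit".
- **Section 8.2.4:** names the tests for binary, continuous and time-to-event secondary endpoints. It gives no order, no dependence on the primary, no division of alpha and no nominal label. It leaves missing data and medication failures to the SAP.
- **Section 8.3:** the only remark on type 1 error. It concerns the absence of an interim analysis in the proof-of-concept part.

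**The concern.** An overall level of 0.10 and a superiority hypothesis tested at 0.10 on every endpoint cannot both describe the same set of tests. With one test and no interim analysis, 0.10 is right for SRI-4 at Day 210. Once the same hypothesis is put on all the secondary and exploratory endpoints with nothing linking them to the primary, 0.10 no longer describes the set.

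The stake is how the result is read. Nothing in the text prevents a trial that misses its primary endpoint from citing 8.2.3 and the secondary objective in support of a formal superiority statement on a secondary indicator. That would matter for the development decision a proof-of-concept study exists to inform.

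**Working it through.** **The plan's own figure.** Section 8.1 states: "A total of 96 evaluable patients randomized provides 80% power to detect a treatment difference of 29% in SRI-4 response rates at Day 210". Inputs are 62% versus 33%, two-sided 0.10, allocation 2:1.

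- Pooled rate = (0.33 + 2 × 0.62)/3 = 0.5233.
- Placebo n before correction = [1.645 × √(1.5 × 0.5233 × 0.4767) + 0.842 × √(0.33 × 0.67 + 0.62 × 0.38/2)]² / 0.29² = 26.6, so 27, and 27 + 54 = 81 in total.
- With continuity correction, placebo n = (26.6/4) × [1 + √(1 + 6/(26.6 × 2 × 0.29))]² = 31.6, so 32, and 32 + 64 = 96.

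The 96 is reproduced with the continuity correction. Without it, 64:32 gives about 86% power. The calculation covers one test, SRI-4 at Day 210.

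**Counting the secondary tests (section 2.2).** Two counts bracket the reading.

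*One time point each, 20 endpoints:*
- 9 proportions: SRI-4, SRI-5, SRI-6, steroid reduction, BILAG flare, PGA worsening, BICLA, CLASI response, medication failure.
- 7 change measures: CLASI, PGA, swollen, tender and active joints, SLEDAI-2K, damage index.
- 4 others: time to medication failure, mean steroid reduction, longest SRI-4 response, time to first flare.

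*Visits and scales counted separately, about 52 tests.* Table 1 schedules efficacy at nine post-baseline visits, Days 30 to 270, and section 6.3.4.3 sets BICLA at three days.
- SRI-4 at the 8 visits other than Day 210: 8
- SRI-5 and SRI-6 at 9 visits each: 18
- BICLA: 3
- Change and percent change for 7 measures: 14
- The remaining single endpoints (5 proportions and 4 others): 9
- Total: 8 + 18 + 3 + 14 + 9 = 52

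The exploratory endpoints are redacted and are left out.

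**Error under no drug effect.** Two-sided p < 0.10 in the drug's favour has probability 0.05 per test. The expected number of such results is 20 × 0.05 = 1.0 or 52 × 0.05 = 2.6, whatever the correlation.

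The chance of at least one is 1 − 0.95^k if the tests are independent. With common correlation ρ between normal test statistics it is 1 − ∫ φ(x) Φ((1.645 − √ρ·x)/√(1 − ρ))^k dx. The correlations are assumptions, since the protocol gives none.

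| ρ (assumed) | 20 endpoints | about 52 tests |
|---|---|---|
| 0 | 64% | 93% |
| 0.3 | 45% | 64% |
| 0.5 | 34% | 47% |
| 0.7 | 24% | 32% |
| one test | 5% | 5% |

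A more realistic structure for the 52 tests has higher correlation within an endpoint than between endpoints. Between/within values of 0.3/0.7, 0.5/0.8 and 0.7/0.9 give 59%, 44% and 29%.

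For p < 0.10 in either direction, the quantity comparable with an overall 0.10, 20 endpoints give 88% at ρ = 0 and 48% at ρ = 0.7, against 10% for one test.

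**The case against.** **The exception clause and the SAP.** Both statements of the level allow for something stated otherwise, and a multiplicity procedure for secondary endpoints is commonly left to the SAP, which is not at hand. This bars any complaint that a hierarchy is simply missing. It does not remove the point: 8.2.3 itself puts the other endpoints under the primary hypothesis, and the protocol states no other level. An SAP that added a hierarchy would have to override that sentence.

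**What 'overall' covers.** It could mean across interim and final analyses, since section 8.3 speaks of type 1 error only in that sense. The reading is possible and leaves the primary test correct. But the text does not say so, and the secondary endpoints are tested at the same level without qualification.

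**How far the 8.2.3 sentence goes.** The explicit rule for declaring superiority is written for SRI-4. The sentence on other endpoints speaks of evaluating them under the same hypothesis and does not repeat the threshold. That formal superiority would be declared on each endpoint is therefore an inference. It is a reasonable one given the secondary objective. The protocol nowhere says that a failed primary would be followed by secondary claims; it merely does not exclude it.

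**Whether a false result is likely.** A reader might infer that a chance finding of superiority is very probable. That rests on independence, which cannot hold here: SRI-4, SRI-5 and SRI-6 are nested, the same patients are scored repeatedly, and change and percent change share one measurement. At a correlation of 0.5 or more in the table the chance is below one half.

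**Custom.** Unadjusted secondary tests are common in proof-of-concept trials, and this point does not object to them as such.

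**Conclusion.** The point holds as a fault in what the protocol states. The 0.10 is the error rate of the SRI-4 Day 210 test alone, while the text calls it overall and applies the same superiority hypothesis, ungated, to all other efficacy endpoints.

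The size rests on an assumed common correlation and on the counting rule, so it has to be given as a range: 24% to 64% on the smaller count and 32% to 93% on the larger. Even the lowest of these is nearly five times the single-test 5%.

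It would be wrong to infer that the primary conclusion is compromised. It is one test at one dose with no interim look in the proof-of-concept part, and the sample size stands.

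**What to change.** 1. In section 8 and in the synopsis, state that the two-sided 0.10 level applies to the single primary test, SRI-4 response at Day 210.
2. Replace the last sentence of 8.2.3 with a statement that p-values for secondary and exploratory endpoints are nominal and support no formal superiority claim. If formal secondary claims are wanted, name instead a short fixed sequence, each step at two-sided 0.10 and tested only after a significant primary result, with everything outside it nominal. That holds the error over the primary and the sequence at 0.10.
3. Align the verb of the secondary objective in section 2.2 and the synopsis with whichever choice is made.

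The change is wording only. The primary test, the 96 evaluable patients and trial conduct stay as they are. The sponsor gives up formal superiority claims on ungated secondary endpoints.

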8.2.4 Secondary Efficacy Endpoint(s)

Binary efficacy endpoints will be assessed via Pearson's chi-squared analysis. Continuous efficacy endpoints will be assessed via analysis of variance (ANOVA) or analysis of covariance (ANCOVA) and treatment will be compared using the F-test. Repeated measures mixed models may be performed to evaluate data collected at each visit and overall. Time-to-event endpoints will be assessed via Kaplan-Meier methodology and treatment will be compared using the log-rank test. The secondary efficacy endpoints will be analyzed on the FAS and if needed repeated in the PP analysis set. Details including handling of missing data and "medication failures" will be available in the SAP.

8.2.5 Analysis of Safety

8.2.5.1 Safety Analysis

Safety analyses will be performed on the SS. AE data will be coded to system organ class and preferred term using MedDRA. The number and percentage of patients experiencing any treatment-emergent AE, overall, and by system organ class and preferred term, will be tabulated. Treatment-emergent AEs will also be summarized by severity and relationship.

Concomitant medications will be coded using the WHO Drug dictionary. Observed values and changes from baseline in vital signs, ECG readings, and hematology and clinical chemistry parameters will be summarized at each individual visit.

8.2.6 Pharmacokinetic and Pharmacodynamic Data

8.2.6.1 Analysis of Pharmacokinetic Data

PK parameters will be calculated from concentration data collected during the MAD phase 1b portion of the study using non-compartmental analysis and include the following:

- C_{max} , T_{max} , AUC, $t_{1/2}$, CL, V_d

The PK parameter data will be listed and summarized descriptively in tabular format.

If data permit, the following analyses will be performed for plasma BOS161721 concentration data:

- A listing of all plasma BOS161721 concentrations by patient at actual times post dose;
- A descriptive summary of plasma BOS161721 concentrations. Summary statistics of geometric mean, % coefficient of variation, standard deviation, median, minimum, and maximum will be tabulated by study days with PK assessments.

8.2.6.2 Analysis of Pharmacodynamic Data

The PD parameter data will be listed and summarized descriptively in tabular format.

Exploratory analyses examining the relationship between PD parameters and PK concentration and PK parameters will be performed.

8.2.6.3 Population Pharmacokinetic Analysis or PK/PD Modeling

Plots of individual patient values for each relevant PD parameter on Y-axis and each relevant PK parameter on X-axis will be examined for relationship. If relationships are revealed by these diagnostic plots, PK and PD data from this study may be analyzed using modeling approaches to describe the relationship and may also be pooled with data from other studies to investigate any association between BOS161721 exposure and biomarkers or significant safety endpoints.

8.3 Interim Analysis and Power

One IA is planned for this study and will be conducted at the time of the POC decision for dose selection.

Since there is no IA during the POC part of the study, there is no impact on the type 1 error.

9 ETHICS AND RESPONSIBILITIES

9.1 Good Clinical Practice

The procedures set out in this protocol are designed to ensure that the sponsor and the principal Investigator abide by the principles of the International Council for Harmonisation (ICH) guidelines on GCP and the Declaration of Helsinki (Version 2013). The clinical study also will be carried out in the keeping with national and local legal requirements (in accordance with US IND regulations [21 CFR 56]).

9.2 DMC

This study will use an external DMC. The DMC is an independent committee established to provide oversight of safety considerations in study and to provide advice to the sponsor regarding actions the committee deems necessary for the continuing protection of enrolled patients and those yet to be recruited to the trial as well as for the continuing validity and scientific merit of the study results. The DMC is charged with assessing such actions in light of an acceptable benefit/risk profile for BOS161721. The recommendations made by the DMC (i.e., dose escalation, etc.) will be forwarded to the sponsor for final decision. The sponsor will forward such decisions, which may include summaries of safety data which are not endpoints, to regulatory authorities, as appropriate.

The sponsor will appoint a DMC for the periodic review of available study data. The DMC is an independent group of experts that advises the sponsor and the study Investigators. The members of the DMC serve in an individual capacity and provide their expertise and recommendations. The primary responsibilities of the DMC are to (1) periodically review and evaluate the accumulated study data for participant safety, study conduct, and progress, (2) make recommendations to the sponsor concerning the continuation, modification, or termination of the study and (3) suggest dose for POC portion of the study as described in [Section 3.1.1.3](#).

The DMC considers study-specific data as well as relevant background knowledge about the disease, test agent, or patient population under study. The DMC is responsible for defining its deliberative processes, including event triggers that would call for an unscheduled review, stopping guidelines, unmasking (unblinding), and voting procedures prior to initiating any data review. The DMC is also responsible for maintaining the confidentiality of its internal discussions and activities as well as the contents of reports provided to it.

The DMC will have access to unblinded treatment information during the clinical trial. Details regarding management and process of this committee are found in the DMC Charter.

The DMC may recommend termination of BOS161721 treatment arm or the entire BOS161721 MAD/POC trial for any safety concern that is felt to outweigh potential

benefits. The recommendation must be supported by the sponsor as indicated in the DMC Charter.

9.3 Institutional Review Board/Independent Ethics Committee

Independent Ethics Committees/IRB must meet the guidelines set out by the U. S. Food and Drug Administration (FDA) and conform to local laws and customs where appropriate. Written IRB/IEC approval for the protocol and the signed ICF must be obtained and transmitted to Boston Pharmaceuticals or representative before the study can be initiated. The IRB/IEC must be informed of and approve all protocol amendments. The Investigator will ensure that this study is conducted in full conformance with all applicable local and regional laws and regulations. The complete text of the World Medical Association Declaration of Helsinki is given in [Appendix 2](#).

